5.4.2 Adverse Events

5.4.2.1 Data considerations

Pre-existing conditions that are detected prior to administration of the first dose of study drug will be recorded as part of the medical history. For all subjects, the AE and SAE reporting period will start with the signature of the ICF and will end with the last study visit (i.e., SFU, Week 12 Visit).

In addition, AEs will be classified for severity according to the Common Terminology Criteria for Adverse Events (CTCAE) Version 5 or later (United States Department of Health and Human Services, Version 5.0, November 17, 2017). For any AEs where it is not possible to provide a CTCAE grading, the events will be assessed using a standard intensity classification (mild, moderate and severe). These will be tabulated together with the AEs that were not classified according to CTCAE criteria i.e., all Grade 1 AEs as per CTCAE criteria will be included in the ‘mild’ category together with those AEs classified as mild as per the ‘standard’ intensity classification.

The CTCAE displays Grades 1 through 5 with unique clinical descriptions of severity for each AE based on this general guideline:

- Grade 1 Mild; asymptomatic or mild symptoms; clinical or diagnostic observations only; intervention not indicated.
- Grade 2 Moderate; minimal, local or noninvasive intervention indicated; limiting age-appropriate instrumental activities of daily living.
Note: instrumental activity of daily living refers to preparing meals, shopping for groceries or clothes, using the telephone, managing money, etc.
- Grade 3 Severe or medically significant but not immediately life-threatening; hospitalization or prolongation of hospitalization indicated; disabling; limiting self care activities of daily living.
Note: self care activities of daily living refer to bathing, dressing and undressing, feeding self, using the toilet, taking medications, and not bedridden
- Grade 4 Life-threatening consequences; urgent intervention indicated.
- Grade 5 Death related to AE.

For the purpose of the tabulations AE intensity categories will be mapped to CTCAE severity classifications grade 1 to 5 as described below:

- Mild – Grade 1
- Moderate – Grade 2
- Severe – Grade 3, 4, 5, where
 - Grade 4 will be derived from the SAE monitoring form, when SAE is life threatening.
 - Grade 5 will be derived from the SAE monitoring form when SAE is fatal.

A TEAE is defined as an AE starting on or after the time of first administration of IMP and up to and including 40 days after the final dose (or last contact depending on which occurs first). Adverse events starting before the date of the first administration of IMP will not be considered TEAEs.

Where dates are missing or partially missing, AEs will be assumed to be treatment-emergent unless evidence exists that does not allow the AE to be treatment-emergent. Handling of missing dates for classification of AEs as TEAEs is described in Section 5.1.1.10.

A TEAE will be counted as a TEAE related to IMP if the response to the question “Relationship to Study Medication” is “Related”.

Severe TEAEs are those with CTCAE Grade 3 or above, or those without a CTCAE grading classified as ‘severe’ by the Investigator.

AEs will be presented as “number of participants (percentage of participants) [number of events]”. In this style of output, “[number of events]” will include all cases of an AE including repeat occurrences in individual participants, while “number of participants” will count each participant only once.

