## **9.4       Planned safety and other analyses**

### **9.4.1       Safety analyses**

Safety analyses will be performed on the Safety Set.

Adverse events will be coded using the Medical Dictionary for Regulatory Activities. A TEAE is defined as any event that was not present prior to the first administration of study medication or any unresolved event already present before the first administration of study medication that worsens in intensity following exposure to treatment. Incidence rates for TEAEs will be summarized overall, by maximum severity, and by relationship to study medication. Serious AEs will also be summarized.

Laboratory evaluations, physical examinations, and ECG will be presented in listings and summarized over time. In this study, the clinical laboratory, physical examination, and ECG assessments conducted at Screening will be considered the baseline values for evaluating of the other safety endpoints.

A by-participant listing of the C-SSRS questionnaire data will be provided.

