1 INTRODUCTION

The purpose of this statistical analysis plan (SAP) is to provide all information that is necessary to perform the statistical analyses of study MG0017. It also defines the summary tables, figures and listings (TFLs) to be included in the Clinical Study Report (CSR) according to the protocol.

This SAP includes safety, efficacy, pharmacokinetics (PK) and pharmacodynamics (PD) analyses. Changes to protocol-planned analysis are documented in Section 6.3. Table, Figure and Listing specifications are contained in a separate document.

This SAP is based upon and assumes familiarity with protocol amendment 3.0 dated 30 November 2022.

If a future protocol amendment necessitates a substantial change to the statistical analysis of study data, this SAP may be amended accordingly. The content of this SAP is compatible with the International Council for Harmonization (ICH)/Food and Drug Administration (FDA) E9 Guidance documents.

The statistical analyses and production of the outputs described in the SAP will be conducted using SAS software version 9.4 or above. The final analyses and outputs will be approved by UCB.

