Note: Discharge date refers to the date of the end of study visit for completed participants or for participants that were withdrawn. For any AEs with known start date after the date of discontinuation, the date of last contact will be used as the discharge date. For participants still ongoing in the study at the time of the data cut-off, and for whom no discharge date is available, the date of the data cut-off will be used instead of the discharge date.

In the event of ambiguity or incomplete data which makes it impossible to determine whether a medication was concomitant or not, the medication will be considered as concomitant. Any medication with a start date on the first dosing date, will be assumed to be concomitant. In the event of ambiguity or incomplete data which makes it impossible to determine whether an adverse event was treatment-emergent or not, the adverse event will be considered as treatment-emergent.

Imputed AE dates will be used for the calculation of duration of AEs, defined as:

Duration of AE = stop date – start date + 1.

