6.3 Appendix 3: Changes to Protocol-Planned Analyses

The description of compliance has been added.

More precision on the model used for the main secondary endpoint strategy (MMRM followed by a One-Sample t-test on the LS Means) were given.

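### The SAP's TEAE definition excludes every AE that starts before first dose, while the protocol counts those that worsen in intensity, and SAP 6.3 does not declare the change

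*SAP*

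**What the plan says.** Protocol 9.4.1 gives the TEAE definition two limbs. The first is an event absent before first dose. The second is "any unresolved event already present before the first administration of study medication that worsens in intensity following exposure to treatment".

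SAP 5.4.2.1 has one limb: the AE starts at or after first dose and no later than 40 days after the last dose (or last contact, if sooner). It then closes the door on the rest: "Adverse events starting before the date of the first administration of IMP will not be considered TEAEs". It makes no exception for worsening.

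SAP 5.4.2.1 also says that "the AE and SAE reporting period will start with the signature of the ICF", so AEs are collected before dosing, and that "Pre-existing conditions that are detected prior to administration of the first dose of study drug will be recorded as part of the medical history".

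On departures from the protocol, SAP section 1 says: "Changes to protocol-planned analysis are documented in Section 6.3". Section 6.3 has two entries: "The description of compliance has been added" and "More precision on the model used for the main secondary endpoint strategy (MMRM followed by a One-Sample t-test on the LS Means) were given". Neither concerns the TEAE definition. The SAP version history does not mention it either, although Amendment 3.0 corrected the treatment-emergent rules for laboratory and ECG abnormalities.

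**The concern.** The trial's primary objective is the safety and tolerability of switching from an IV C5 inhibitor to zilucoplan. AEs are collected from consent, and first dose follows about 2 weeks (eculizumab) or 8 weeks (ravulizumab) after the Screening Visit. An AE can therefore begin in Screening, still be present at the switch, and become more severe on zilucoplan. The protocol counts that event as treatment-emergent. The SAP, read literally, does not.

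Both primary endpoints (TEAEs, and TEAEs leading to withdrawal of study medication) and the secondary serious-TEAE endpoint use this definition. Protocol 8.3 also makes TEAEs and treatment-emergent SAEs the basis of registry disclosure. A reader who checks SAP 6.3 for departures from the protocol would conclude that there is none here.

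**Working it through.** The plan gives no figure on this point to reproduce. The check is a comparison of wording, followed by arithmetic for scale only.

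**Step 1. Apply both definitions to the possible cases.**

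| Case | Protocol 9.4.1 | SAP 5.4.2.1 |
|---|---|---|
| AE starts after first dose, inside the 40-day window | TEAE | TEAE |
| AE starts before first dose, unresolved, then worsens in intensity; worsening entered as a new AE record with a post-dose start | TEAE | TEAE, through the new record |
| Same event; worsening kept on the original record | TEAE | Not a TEAE |
| AE starts before first dose and leads to stopping or becomes serious at unchanged intensity | Not a TEAE | Not a TEAE |

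The definitions part in the third row only.

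**Step 2. Look for a SAP rule that restores the third row.** SAP 5.1.1.10 defaults to treatment-emergent where ambiguity or incomplete data make it "impossible to determine whether an adverse event was treatment-emergent or not, the adverse event will be considered as treatment-emergent". SAP 5.4.2.1 repeats the default for missing or partial dates. A known pre-dose start date is neither missing nor ambiguous, so neither rule applies.

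**Step 3. Ask which row a site would produce.**
- Towards a new record: protocol 8.2.1 has worsened findings recorded as AEs; protocol 8.3.1 requires worsened AEs to be reported; Appendix 3 (protocol 10.3) treats exacerbation of a pre-existing condition as an AE and assigns each AE one intensity category; SAP 5.4.2.1 sends pre-existing conditions to medical history.
- Towards the original record: the follow-up rules in Appendix 3 put updated information in the eCRF originally completed. This is weaker, because it refers to the eCRF and not to a single AE line.
- Neither is required. Protocol 10.1.6.1 leaves the detail to eCRF completion guidelines, which are not among the documents.

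**Step 4. Scale, with the planned n = 20.** The number of affected participants is unknown. If k participants have such an event as their only TEAE, the SAP rule lowers TEAE incidence by k/20:
- k = 1: 1/20 = 5.0 percentage points
- k = 2: 2/20 = 10.0 points
- k = 3: 3/20 = 15.0 points

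A participant with any other TEAE contributes 0.

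For TEAEs leading to withdrawal of study medication, one such event separates 0/20 from 1/20. The exact (Clopper-Pearson) 95% limits are:
- 0/20: upper limit 1 − 0.025^(1/20) = 16.8%, so 0 to 16.8%
- 1/20: estimate 5.0%, limits 0.1% to 24.9%

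This illustrates the sensitivity of a count at n = 20. It is not evidence that an event will be lost.

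**The case against.** The strongest reply is that the SAP's start-date rule is how the protocol's second limb would work in practice. If a worsening is a new AE with its own start date, SAP 5.4.2.1 already counts it, and for conditions held in medical history that is the only way it can enter the AE data. On this reading few events, or none, are lost. Much of this stands: it is the better-supported reading and it limits the likely effect. It does not remove the conflict, because no passage requires a new record and the SAP does not say that it relies on one.

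The remaining group is also narrow. The event must start between consent and first dose, be recorded as an AE, stay unresolved, worsen in intensity after dosing and not receive a new record. Entry rules shrink the pool: exclusion 5 bars systemic infection in the 2 weeks before Baseline, and inclusion 6 bars an MG-ADL change of more than 2 points between Screening and Baseline.

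Other outputs do not depend on the TEAE definition. SAP 5.2 summarises study discontinuations due to AEs. SAP 5.4.2.2 counts all deaths and lists all AEs and permanent withdrawals of IMP due to AEs. Laboratory and ECG shift displays show worsening from Baseline however AEs are dated. So some of these events would still be seen. They would not be in the primary endpoint counts.

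Two stronger readings are tempting. A reader might infer that the primary endpoints will be materially undercounted; the documents give no basis for any number, and the loss may be nil. A reader might also infer that the SAP drops pre-dose AEs that later lead to stopping or become serious; the protocol's limb covers worsening in intensity only, so at unchanged intensity such events fall outside both definitions.

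**Conclusion.** The contradiction is in the text and is undeclared. It sits in the definition behind both primary endpoints and the serious-TEAE endpoint, so it should be fixed and not left to interpretation. The direction is certain: dropping the limb can only lower TEAE counts. The size is unknown and depends on a recording convention that the documents do not state; if every post-dose worsening is entered as a new record, the effect is zero. No hypothesis test is affected, since the only one planned is on MG-ADL (SAP section 2) and the safety endpoints are descriptive.

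**What to change.** In SAP 5.4.2.1:

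1. Restore the protocol limb: *An AE unresolved at first dose that worsens in intensity on or after first dose, within the 40-day window, is counted as one TEAE, with onset at the date of worsening and the worsened intensity; the original pre-dose record is not itself counted.* The last clause prevents double counting in the number of events when an original and a new record both exist.
2. Limit the exclusion sentence to pre-dose AEs that do not worsen in intensity after first dose.
3. State one recording convention: a worsening is entered as a new AE record dated at the worsening. Any worsening held only on an original record is resolved by data query before database lock, because a single intensity category per AE gives neither the date nor the level of the increase.

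The 40-day window stays as written. If the sponsor intends the narrower definition, the alternative is to declare and justify it in SAP 6.3.

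The cost is a few sentences of SAP text. The new-record convention needs no eCRF change, visit or participant. Queries on original records are a small cost with 20 participants.

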5.4.2.2 AE summaries

1. A TEAE overview table will be provided by treatment group, including the number, percentage of participants and frequency of the following TEAEs:
 - Any TEAEs
 - Any TEAEs above 5% of occurrence
 - Serious TEAEs
 - TEAEs leading to permanent withdrawal from IMP
 - Treatment-related TEAEs
 - Severe TEAEs
 - TEAEs leading to death
 - All deaths (AEs leading to death)
2. The number, percentage of participants and frequency of the following TEAEs will be summarized by System Organ Class (SOC), high level term (HLT), and PT:
 - Serious TEAEs

- Non-serious TEAEs
- TEAEs leading to death

In case of 5 or less of the following TEAEs, no summary table will be displayed, and the listing of AEs will be used. In case of 6 events or more the number, percentage of participants and frequency of the following TEAEs will be summarized by System Organ Class (SOC), high level term (HLT), and PT:

- Any TEAEs
 - Severe TEAEs
 - TEAEs leading to permanent withdrawal from IMP
 - Treatment-related TEAEs leading to permanent withdrawal from IMP
3. The number, percentage of participants with TEAEs will be summarized by maximum intensity (mild, moderate and severe), SOC, and PT as well as by intensity (mild, moderate and severe), SOC, and PT.
4. The number, percentage of participants and frequency of the following TEAEs will be summarized by relationship, SOC, HLT, and PT:
- Any TEAEs
 - Serious TEAEs
 - Fatal TEAEs

For these summaries, the number and percentage of participants who experienced at least one TEAE as well as the number and percentage of participants who experienced each specific SOC, HLT (if HLT is presented) and PT will be presented. The corresponding number of TEAEs will also be presented for the Overall Summary of TEAEs table. For the presentation of TEAE incidences, the SOCs will be sorted alphabetically, and HLT within SOC – (if HLT is presented), and within HLT, the PT will be used and presented by decreasing total frequency.

Listings of all AEs in (ES), permanent withdrawal of IMP due to AEs, participant discontinuation from study due to AEs, AEs leading to death will be presented by participants in SS.

To assess the impact of the COVID-19 pandemic on safety, additional summaries and listings will be presented. All COVID-19 related TEAEs will be summarized by MedDRA SOC, HLT and PT.

Study participants with a confirmed or suspected COVID-19 infection were identified by searching TEAEs for selected MedDRA terms as defined in Section 6.1.9 and described as “COVID-19 related TEAEs.

A separate listing of all COVID-19 related AEs will be presented in SS.

In addition, all listing of AEs will include a column for COVID-19 relatedness.

Since the beginning of the COVID-19 pandemic, the COVID-19 vaccination followed a specific mass vaccination program in a short time frame. Administration of doses of COVID-19 vaccination might be needed during this study and is likely to increase the reporting of AEs.

Vaccination might have an impact on the safety reporting in the non-COVID-19 vaccine clinical trials. Due to this, the potential impact of concomitant COVID-19 vaccination on the current trial may be different from other types of concomitant drugs and established vaccination, due to the frequency of potential events related to the COVID-19 vaccination and the evolving safety profile of these new vaccines. To control the potential bias arising when an important proportion of the vaccinated participants reported AEs to vaccination (which inappropriately may be captured as adverse reactions in the product information) additional safety outputs within the frame of sensitivity analysis will be created.

Additional sensitivity safety analysis with outputs presenting the TEAEs occurred when participants were considered as not at risk of TEAEs related to COVID-19 vaccination is proposed. The approach of interval censoring will be employed: interval censoring between COVID-19 vaccination date and a pre-specified period in which participants are considered as at risk for COVID-19 vaccination related AEs. A 7-day period may allow the removal of the potentially most frequently reported AEs related to COVID-19 vaccines. In such outputs, all TEAE data will be included, with the exception of the events occurred within the defined window of 7 days post COVID-19 vaccination(s) for those participants vaccinated during the study and all TEAE data for those participants not vaccinated during the study.

All AEs within a 7-day period post each COVID-19 vaccination will be summarized for all vaccinated participants. Two separate listings will display the AEs after adjustment of the interval censoring and the concomitant COVID-19 vaccination.

All AEs after a 7-day period of each COVID-19 vaccination will be listed for all vaccinated participants. Two separate listings will display the AEs after adjustment of the interval censoring and the concomitant COVID-19 vaccination.

At all the outputs referring to the interval vaccination censoring, the following footnote will be incorporated: “COVID-19 Vaccination Interval Censored (TE)AEs exclude those (TE)AEs occurred within the pre-specified time period of 7 days post COVID-19 vaccination(s) for each participant, if applicable.”

5.4.3 Other Safety Assessments

Other safety assessments (AE of special interest, Laboratory data and Vital Signs) will also be performed in the SS.

5.4.3.1 AEs of Special Interest and AEs of Interest

The AEs of Special Interest identified in this study are the Hy's Law that are described in Section 5.4.3.2.4.

The following are AEs of Interest (as defined in Section 6.1.6 that require special statistical analyses:

- Hypersensitivity reactions
- Anaphylactic reactions
- Injection site reactions
- Drug related hepatic disorders
- Malignancies or unspecified tumors

The number and percentage of participants who experience each AE of Interest will be summarized separately for each AE of interest. The following summaries will be presented:

- Incidence of AEIs and serious AEIs by SOC and PT (serious and non-serious will appear in the same table)
- Incidence of AEIs by relationship, SOC and PT
- Incidence of AEIs by maximum intensity (mild, moderate and severe), SOC and PT.

5.4.3.2 Clinical laboratory evaluations

The following table (Table 5.1) lists hematology, chemistry and coagulation analytes that are collected throughout the study, using a central laboratory and following the schedule of assessments according to the protocol.

Table 5.1: Protocol-required safety laboratory assessments

Laboratory assessments	Parameters			
Hematology	Platelet count	RBC indices: MCV MCH %Reticulocytes	WBC count with differential: Neutrophils Lymphocytes Monocytes Eosinophils Basophils	
	RBC count			
	Hemoglobin			
	Hematocrit			
Clinical chemistry ^a	BUN	Potassium	AST/SGOT	Total and direct bilirubin
	Creatinine	Sodium	ALT/SGPT	Total protein
	Glucose	Calcium	Alkaline phosphatase	Amylase
	Lipase			
Routine urinalysis	
• Specific gravity• pH, glucose, protein, blood, ketones, bilirubin, urobilinogen, nitrite, leukocyte esterase by dipstick• Microscopic examination (if blood or protein is abnormal)			
Other screening tests	
• Follicle-stimulating hormone and estradiol (as needed in women of non-childbearing potential only)• Serum hCG pregnancy test (as needed for women of childbearing potential)^b 
The results of each test must be entered into the eCRF.
			

ALT=alanine aminotransferase; AST=aspartate aminotransferase; BUN=blood urea nitrogen; eCRF=electronic Case Report form; HBsAg=hepatitis B surface antigen; hCG=human chorionic gonadotropin; INR=international normalized ratio; IRB=Institutional Review Board; MCH=mean corpuscular hemoglobin; MCV=mean corpuscular volume; RBC=red blood cell; SAE=serious adverse event; SGOT=serum glutamic-oxaloacetic transaminase; SGPT=serum glutamic-pyruvic transaminase; ULN=upper limit of normal; WBC=white blood cell

^a Details of liver chemistry stopping criteria and required actions and follow-up assessments after liver stopping or monitoring event are given in the protocol. All events of ALT $\geq 3 \times$ ULN and bilirubin $\geq 2 \times$ ULN ($>35\%$ direct

Table 5.1: Protocol-required safety laboratory assessments

Laboratory assessments	Parameters
------------------------	------------

bilirubin) or ALT $\geq 3 \times \text{ULN}$ and INR > 1.5 , if INR measured, may indicate severe liver injury (possible Hy's Law) and must be reported as an SAE (excluding studies of hepatic impairment or cirrhosis).

^b Local urine testing will be performed at visits subsequent to the Screening Visit.

All laboratory samples are collected prior to IMP administration at applicable visits.

